Randomisation is proposed as there are insufficient historical data on which to base estimates of the “average” reduction in dexamethasone dose in this population over the study period nor of the variability in that dose. Statistical comparison of dexamethasone dosing in the control and micronised progesterone arms is not planned. The control arm will, however, act as a comparator when evaluating dexamethasone dosing in the progesterone arm. While this study is not powered to perform formal statistical analyses, we plan to carry out exploratory work to compare the (i) cumulative dexamethasone dose (ANOVA/t-test or Mann Whitney U if the data are not normal); (ii) final dexamethasone dose (ordered logistic regression) and (iii) time to reach final dose in each arm (Cox regression). The comparator arm will also aid statistical design of the planned, subsequent definitive efficacy trial. Patients in the control arm will receive placebo provided by the manufacturer. This number of patients was chosen empirically, but is similar to the size of a typical “expansion cohort” in Phase 1 oncology trials that seek to better characterise toxicity and inform the design of a future trial; the use of such cohorts appears to increase the likelihood of success in that future trial (60).

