11.2 Dexamethasone (standard care – non IMP)

Dexamethasone is also prescribed to patients in the PROSSPER trial but is the non IMP and will be supplied from hospital stock.

Dexamethasone will be prescribed as standard of care taken orally in the morning within 30 minutes of finishing breakfast.

At time of randomisation, patients must have been on 4mg-12mg of dexamethasone for at \geq 48 hours.

Stage 1: Day 1 – 10 (Please refer to Appendix No.6 - Doses Stage 1)

Pharmacokinetic sampling days are Day 1 and one other day between Days 5 and 10. This day will be decided by the clinical team and patient

On Day 1, patients will take 8mg dexamethasone in the morning.

On Days 2-10, patients will take dexamethasone in the morning as clinically indicated, except on the second pharmacokinetic sampling day when the dose of dexamethasone will be 8mg.

Stage 2: Day 1 – 22 (Please refer to Appendix No.7 - Doses Stage 2)

On Day 1, patients will take 8mg dexamethasone in the morning.

From Day 3-14, if clinically appropriate, the dexamethasone dose will be reduced by 2mg/day on alternate days (see Appendix 6 [Drug Table Stage 1] and Appendix 7 [Drug Table Stage 2]) and can be discontinued if indicated.

Should symptoms of raised intracranial pressure recur, the dose of dexamethasone will be increased by 4mg (i.e. to 2mg above the dose at which the patient's symptoms had been controlled).

Once the dose has been re-escalated, and after Day 14, subsequent dose adjustments will be at the clinician's discretion.

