14.3 Data Collection

Data generated will be entered by site staff onto a Trial specific eCRF. SCTRU will be responsible for checking the data, and validating it. All source data should be recorded within patient files.

The data collected will include:

- initial clinical details at randomisation
- drug administration (progesterone/placebo and dexamethasone) including concomitant medications
- adverse events
- blood tests (see Appendices 4 & 5) including endocrine studies
- ongoing clinical details during study period
- patient questionnaires

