15 STATISTICS

15.3 Sample Size

In the absence of data necessary to make an informed power calculation for the secondary efficacy endpoint, this sample size for this study was arrived at empirically but is supported by clinical experience and/or simulated data, as outlined below.

In a group of 36 patients randomised 1:1 between intervention and control we would have 90% power to demonstrate an effect size of -1.00 between the two groups, and 80% power to demonstrate a difference of -0.85. In the context of the endpoint being final dexamethasone dose on Day 14, scenarios that would result in this effect size or greater are clinically reasonable (see below).

Final Dexamethasone dose	
+ placebo	+ progesterone

Mean	SD	Mean	SD	SD (pooled)	Effect size	N (per arm)	N (total)
4	2	2	2	2	-1.0	18	36
4	1	2	1	1	-2.0	6	12
2	1	1	1	1	-1.0	18	36

To further illustrate the potential effect sizes that we would be able to identify, and to assess the power that $n=36$ would provide for the *cumulative* dose of dexamethasone across the study period, simulated data have been generated, based on assumptions drawn from clinical experience. In these data the mean effect size (1000 simulations) for the final and cumulative dexamethasone doses was -0.88 and -1.04 respectively. The power that we have to detect effect sizes of this magnitude with $n=18$ (per arm) is 83.05% and 92.13% respectively.

A one sided t-test was used to calculate the sample size as we are testing specifically for reduction rather than a difference. The one sided t-test is exploratory and the primary outcome is safety.

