15.4 Randomisation and Stratification

After ensuring that the patients meet **all** eligibility criteria and has consented to participate in the study, sites will randomise the patient following the instructions described in the PROSSPER work instructions for sites. Once a patient has been randomised, a patient study number will be issued and this should be used in all correspondence.

Stage 2 of the PROSSPER trial will be randomised into two treatment groups: Progesterone arm or placebo arm. Randomisation will be a 1:1 allocation; 18 patients in each group stratified by clinical site (Leeds and Liverpool).

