15.5 Analysis Plan

The final analysis will be performed on the evaluable population (that is, patients who successfully completed the 14-day treatment period and were not subsequently found to be ineligible); no interim analysis is planned. Unless otherwise stated, 80% confidence intervals will be used; 1-sided p-values calculated and $\alpha=0.05$ as a threshold for significance. Substantial missing data (i.e., missing in >10% patients) will be highlighted in statistical study reports but not imputed. A full statistical analysis plan will be developed prior to any analyses being performed.

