14.4 Final analysis

The final analyses will be performed once the end of study has been declared. They will address each endpoint explicitly with evidence, including:

- Stage 1, primary endpoint (Section 2.2.1.1 Primary:) – to be assessed at end of Stage 1
 - Percentage of target exposure for each patient will be calculated and presented. Subsequent counts of number of patients to achieve 50-150% of target exposure will be presented.
- Stage 2, primary endpoint (Section 2.2.2.1 Primary:) – to be assessed at end of Stage 2
 - Number of patients tolerating progesterone until the end of the 14-day treatment period will be calculated and presented. Note that at least 13/18 patients should

be identified as tolerating progesterone (i.e., ensuring that >50% patients, using 80% CI, tolerate the treatment).

- Stage 2, secondary endpoint (Section 2.2.2.2 Secondary) – to be assessed at end of Stage 2
 - Compliance data will be presented and the number of patients complying with protocol guidelines on dose reduction will be calculated and presented. Note that at least 13/18 patients should be identified as complying with the dose reduction guidelines, to demonstrate compliance (i.e., ensuring that >50% patients, using 80% CI, comply).
 - Dexamethasone related side-effects will be coded according to the CTCAE toxicity criteria. These data will be presented in several ways, including worst value over the trial period for each patient and tabulation of all side-effects graded \geq grade 1 in at least 10% of patients.
 - Presentation/analysis of QoL (DSQ-C, EORTC QLQ-30 & BN20) data.
 - Calculation of percentage reduction in dexamethasone at Day 14.
 - Comparison of final dexamethasone dose in the progesterone and placebo arms (e.g., by ordered logistic regression).
 - Comparison of cumulative dexamethasone dose in the progesterone and placebo arms (e.g. by ANOVA/t-test or Mann Whitney U if normality assumptions are violated).
 - Comparison of time to reach final dose in each arm in the progesterone and placebo arms (e.g., Cox regression).
- Stage 2, tertiary endpoint (Section 2.2.2.3 Tertiary) – to be assessed at end of Stage 2
 - Presentation of relevant lab results to assess endocrine, liver function and lipid profiles in patients on progesterone.
 - Comparison (progesterone v placebo) of CT/MRI data (including tumour size, enhancement pattern etc)

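### Cumulative dexamethasone dose is to be compared without adjustment, by a t-test or a rank test chosen from the data; one pre-set linear model that includes the pre-study dose would fix the effect measure at almost no cost.

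*Protocol*

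**What the plan says.** Section 2 (Aims and endpoints) lists among the exploratory comparisons "cumulative dexamethasone dose (ANOVA/t-test or Mann Whitney U if the data are not normal". Section 14.4 Final analysis repeats this, but as an example: "Comparison of cumulative dexamethasone dose in the progesterone and placebo arms (e.g. by ANOVA/t-test or Mann Whitney U if normality assumptions are violated". The other two comparisons are final dose by ordered logistic regression and time to final dose by Cox regression. No covariate is named for any of the three, not even the stratification factor: "Randomisation will be a 1:1 allocation; 18 patients in each group stratified by clinical site (Leeds and Liverpool".

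On the dose before the trial, section 11.2 states: "At time of randomisation, patients must have been on 4mg-12mg of dexamethasone". Sections 3.1.6 and 11.2 then put every Stage 2 patient on 8 mg on Day 1. Section 14.3 lists among the data to be collected "drug administration (progesterone/placebo and dexamethasone) including concomitant medications".

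Section 2 says the control arm will help in designing the later definitive trial. It also says the study is not powered for formal analysis, and section 11.8 says no formal efficacy comparison will be made. Section 15.5 nevertheless sets a one-sided 0.05 level "as a threshold for significance" and promises a full statistical analysis plan before any analysis.

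**The concern.** There are two weaknesses in the stated method for cumulative dose.

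First, the normality condition makes the effect measure depend on the data. A t-test estimates a mean difference in mg. Mann-Whitney U compares ranks and yields neither a mean difference nor an SD in mg, and those are the figures that the design of the next trial needs.

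Second, the fixed 8 mg start makes the on-study baseline dose a constant. The pre-study dose is then the only baseline dose information that differs between patients, and the named tests cannot use it. If it predicts later need, omitting it leaves avoidable variation in the error term of a comparison with only 18 patients per arm.

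**Working it through.** **Is non-normality foreseeable?** Appendix 5 gives the scheduled daily doses as 8, 8, 6, 6, 4, 4, 2, 2 mg on Days 1-8 and 0 on Days 9-14. The total is 2 × (8 + 6 + 4 + 2) = 40 mg. All patients who complete the taper on schedule share this one value. Patients who pause or re-escalate lie above it. A pile-up at 40 mg with a tail to the right is therefore likely, and the switch to the rank test is a real prospect.

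**The plan's own power figures.** Inputs from section 15.3 and 15.5: 18 per arm, one-sided 0.05 ("A one sided t-test was used to calculate the sample size"), and "90% power to demonstrate an effect size of -1.00 between the two groups". Method: noncentral t, 34 df, noncentrality d × √(18/2) = 3d.

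| Effect size d | Stated power | Recomputed |
|---|---|---|
| 1.00 | 90% | 90.2% |
| 0.85 | 80% | 80.3% |
| 0.88 (simulated, final dose) | 83.05% | 82.7% |
| 1.04 (simulated, cumulative dose) | 92.13% | 92.1% |

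The stated figures reproduce on the one-sided basis. A two-sided test would give 83.0% at d = 1.00.

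**Effect of adjusting for one covariate.** Let r be the correlation of pre-study dose with cumulative dose. The protocol gives no value, so r is an assumption. The linear model has 33 df and noncentrality 3d/√(1 − r²). With d = 1.04, 3d = 3.12. The width of the 80% interval (the level in section 15.5), relative to the unadjusted one, is √(1 − r²) × 1.0006, where 1.0006 is the ratio of the t quantiles at 33 and 34 df.

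| Assumed r | Noncentrality | Power at d = 1.04 | Relative interval width |
|---|---|---|---|
| unadjusted | 3.12 | 92.1% | 1 |
| 0 | 3.12 | 92.1% | 1.001 |
| 0.1 | 3.12/√0.99 = 3.14 | 92.3% | 0.996 |
| 0.2 | 3.12/√0.96 = 3.18 | 93.0% | 0.980 |
| 0.3 | 3.12/√0.91 = 3.27 | 94.0% | 0.955 |
| 0.5 | 3.12/√0.75 = 3.60 | 97.0% | 0.867 |

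Site in the model costs one further degree of freedom (36 − 4 = 32), which is not included above.

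**Can the covariate be defined?** Section 11.2 asks for 4-12 mg for at least 48 hours at randomisation. Appendix 5 shows 8 mg on Days -2 and -1. If both columns describe the same two days, the dose just before Day 1 is 8 mg for everyone and carries no information. The two places must be reconciled before the covariate is written down.

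**The case against.** The case against is substantial, and much of it stands.

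- Section 14.4 gives the tests as examples, and section 15.5 leaves detail to an analysis plan that is not shown. No sentence excludes covariates, and ANOVA extends naturally to a covariate model. A missing covariate list is therefore not an error. What remains is the stated choice itself: section 2 names the tests without calling them examples, and both sections let a look at normality select the effect measure.
- A reader might infer that all the dexamethasone comparisons are confined to unadjusted tests. They are not. The t-test and Mann-Whitney wording covers cumulative dose only; the ordered logistic and Cox models can take covariates. The √(1 − r²) narrowing does not carry over to those models, where adding a covariate also changes the quantity estimated.
- A reader might infer that pre-study dose must be prognostic, or is the strongest predictor. Nothing in the protocol shows this. Section 2 says historical data are insufficient even for the average reduction, and section 1.3.2 describes starting high and reducing over days, so the entry dose may partly reflect how far an earlier taper had gone.
- A reader might take a chance imbalance in entry dose as passing straight into the treatment effect. It passes only through the slope, which is unknown, and the unadjusted standard error already allows for such imbalance.
- A reader might take the larger power gain at an effect size of 0.85 (80.3% to 89.2% at r = 0.5). Section 15.3 frames that effect size around final dose. For cumulative dose its figure is 1.04, where power is already 92.1%.
- Means and SDs can be tabulated whichever test is used. That is true, but the inferential result and its interval would still lack a fixed scale.

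**Conclusion.** The point holds for cumulative dose only, and as an improvement rather than an error. The protocol names an unadjusted analysis with a data-driven switch between two effect measures, where the switch is likely to be triggered and the second measure serves the next trial's design poorly. That part depends on no assumed correlation.

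The covariate part is conditional. For assumed correlations of 0.2 to 0.5, intervals narrow by about 2% to 13% and power rises by 0.9 to 4.9 points from 92.1%. Near zero there is practically neither gain nor loss. These figures assume a linear model, one covariate, 18 evaluable patients per arm and the protocol's simulated effect size. The comparison is exploratory and the primary outcome is safety, so no confirmatory claim rests on it.

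**What to change.** In section 2 and section 14.4 Final analysis, replace the t-test/Mann-Whitney choice with one pre-specified linear model for cumulative dexamethasone dose. Its terms are arm, site and pre-study dexamethasone dose, with a permutation or robust p-value so that no normality check is needed. Report the difference in mg with its interval, and keep the unadjusted result as a sensitivity analysis. The same covariate may be added to the ordered logistic model for final dose, without a claim of narrower intervals there.

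Reconcile section 11.2 with the Days -2 and -1 column of Appendix 5, so that the covariate can be defined as the last clinically chosen dose before the fixed 8 mg.

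The cost is wording and one degree of freedom for each of the two added terms. The pre-study dose has to be known for the eligibility check, so little or no extra data collection is needed; the eCRF should hold it as a value.

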2.2.2.2 Secondary

- Compliance with the structured dexamethasone dose reduction guidelines at 75% of decision points in at least 13 of 18 patients in line with protocol guidelines and as clinically appropriate.
- Description of dexamethasone related symptoms and QOL.
- Percentage of patients achieving a $\geq 50\%$ reduction in dexamethasone dose taken on Day 14
- Comparison (progesterone v placebo) of final dexamethasone dose on Day 14

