Appendix 7 – Stage 2: Drug table

Day	DEX dose ¹ (non IMP)	PROG/Placebo dose ² (IMP)	
1	8mg	Xmg	Dose of progesterone (Xmg) will be determined by the pharmacokinetic results of Stage 1
2 – 14	as clinically indicated, using Prossper DEX dosing	as defined by Stage 1. As clinically indicated, using Prossper PROG/Placebo dosing	
15	as clinically indicated, at clinicians discretion		
16	as clinically indicated, at clinicians discretion		
17	as clinically indicated, at clinicians discretion		
18	as clinically indicated, at clinicians discretion		
19	as clinically indicated, at clinicians discretion		
20	as clinically indicated, at clinicians discretion		
21	as clinically indicated, at clinicians discretion		
22	as clinically indicated, at clinicians discretion		

¹ DEX dosing - 8mg, 6mg, 4mg, 2mg, 0mg

From Day 3-14, if clinically appropriate, the dexamethasone dose can be reduced by 2mg/day on alternate days, and can be discontinued if indicated. Should symptoms of raised intracranial pressure recur, the dose of dexamethasone will be increased by 4mg (i.e. to 2mg above the dose at which the patient’s symptoms had been controlled).

² PROG dosing - 600mg t.d.s, 400mg t.d.s, 200mg t.d.s

Any patient unable to tolerate the initial Progesterone/placebo dose would have the dose reduced; if that reduced dose is not tolerated, it will be reduced further. If this second dose is not tolerable, the patient will be withdrawn from the study.

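### The exploratory Cox comparison of time to final dexamethasone dose has no fixed direction of benefit, because the event is each patient's own Day 14 dose

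*Protocol*

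**What the plan says.** Section 2 (Aims and Endpoints) lists three exploratory between-arm comparisons: cumulative dexamethasone dose, final dose, and "time to reach final dose in each arm (Cox regression"). Section 14.4 (Final analysis) repeats the third among the Stage 2 secondary analyses: "Comparison of time to reach final dose in each arm in the progesterone and placebo arms (e.g., Cox regression"). Section 2 also limits their weight: "While this study is not powered to perform formal statistical analyses", the work is exploratory.

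The final dose is the Day 14 dose. The endpoint in Section 2.2.2.2 is "Comparison (progesterone v placebo) of final dexamethasone dose on Day 14".

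The dosing rules that generate the event times are in Section 11.2 and Appendices 5 and 7:
- "From Day 3-14, if clinically appropriate, the dexamethasone dose will be reduced by 2mg/day on alternate days", on the levels "DEX dosing - 8mg, 6mg, 4mg, 2mg, 0mg". Appendix 5 shows 8 mg on Days 1-2, 6 mg from Day 3, 4 mg from Day 5, 2 mg from Day 7 and 0 mg from Day 9.
- "Should symptoms of raised intracranial pressure recur, the dose of dexamethasone will be increased by 4mg".
- "Once the dose has been re-escalated, and after Day 14, subsequent dose adjustments will be at the" clinician's discretion.

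Section 15.5 restricts the final analysis to eligible patients who completed the 14-day treatment period. Unless otherwise stated, it uses 1-sided p-values at a 0.05 threshold.

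**The concern.** A time-to-event comparison can be interpreted only if the event means the same thing for every patient and is either good or bad. Here the event is arrival at a dose that differs between patients and may be 0 mg or the full starting dose. A patient who cannot reduce at all arrives at once, while one who comes off dexamethasone has to go through four steps first.

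The secondary aim in Section 2.1.2 is to measure the extent and duration of dose reduction, and this is the only time-based dexamethasone analysis that serves it. Section 2 says the comparator arm will help design the definitive trial. A hazard ratio whose sign does not track benefit could contradict the final-dose and cumulative-dose results reported next to it. An analysis plan that implements the protocol faithfully would keep the problem, because the protocol itself fixes the event and names the model.

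**Working it through.** **The plan's own figures.** The protocol gives no hazard ratio, event count or power for the Cox comparison. Its Section 15.3 power figures concern a one-sided t-test on dose with 18 per arm. With noncentrality d × √(18/2) = 3d and 34 degrees of freedom, the power is 90.2%, 80.3%, 82.7% and 92.1% at d = 1.00, 0.85, 0.88 and 1.04. The protocol states 90%, 80%, 83.05% and 92.13%, so these reproduce. The first row of its planning table (mean final dose 4 v 2 mg, SD 2) is the base case below.

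**Event day by outcome, from the documents.** Let T be the first day from which the dose equals the Day 14 dose.
- Taper stopped at the last controlled dose: final dose 8, 6, 4, 2, 0 mg gives T = 1, 3, 5, 7, 9. Hence T = 9 − final dose. In this case T is simply the final dose with its sign reversed.
- Recurrence assumed one day after a step, then +4 mg held: failure at 6, 4 or 2 mg gives T = 4, 6 or 8 with final dose 10, 8 or 6 mg, all before the Day 9 of full success. Failure at 0 mg gives T = 10 with final dose 4 mg.

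**Base case (assumed).** The lowest dose that controls symptoms is 0, 2, 4, 6 or 8 mg with probabilities 0.40, 0.30, 0.20, 0.10, 0 on progesterone and 0.05, 0.25, 0.40, 0.25, 0.05 on placebo. If patients stop at that dose, the mean final dose is 2.0 v 4.0 mg. The mean event day is:
- progesterone: 0.40×9 + 0.30×7 + 0.20×5 + 0.10×3 = 7.0
- placebo: 0.05×9 + 0.25×7 + 0.40×5 + 0.25×3 + 0.05×1 = 5.0

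The better arm arrives later. Cox regression, h(t|x) = h0(t)·exp(βx) with HR = exp(β) and Efron ties, gives the following for the base case and for three other assumed distributions: a stronger drug (0.8 v 4.0 mg when stopping), a weaker one (2.4 v 3.5 mg), and failure only at 0 mg (0.6 v 1.4 mg).

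| Behaviour after failure | Base | Stronger | Weaker | Failure only at 0 mg |
|---|---|---|---|---|
| Stop at last controlled dose | 0.38 | 0.28 | 0.70 | 0.56 |
| +4 mg, held | 0.70 | 0.62 | 0.81 | 1.79 |
| +4 mg, re-taper every 2 days | 0.95 | 1.11 | 0.89 | 1.79 |
| +4 mg, re-taper every 4 days | 1.07 | 1.37 | 0.96 | 1.79 |

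In simulated base-case trials of 18 per arm, the stop rule gives HR < 1 in about 100% of trials, nominally significant in the wrong direction in 88%. With +4 mg held, the figures are 91% and 27%. A separately coded stop model at 4 v 2 mg gives 0.46.

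**A different model: constant daily recurrence (assumed).**
- 15% placebo v 5% progesterone, +4 mg held: mean final dose 6.1 v 2.8 mg, HR about 0.8, HR < 1 in roughly 71-76% of trials.
- 25% v 10%, held: HR 0.57.
- 15% v 5%, re-tapered by 2 mg every 4 days to 2 mg above the dose at recurrence: HR about 1.24-1.28.
- 8% v 3%, held: mean final dose 4.1 v 1.8-1.9 mg, close to the protocol's own 4 v 2 mg, HR about 1.0.

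The drug reduces the dexamethasone dose in every one of these cases, yet the hazard ratio runs from 0.28 to 1.79.

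**Check of a common event.** The event is now 4 mg or less reached and held to Day 14, with others censored at Day 14. The base-case HR is 1.67 (stop), 3.23 (+4 mg held) and 2.24 (re-taper). Across the 16 cells of the table it is never below 1. It equals 1.0 where all failures occur at 0 mg, because every patient then reaches and keeps 4 mg or less.

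**The case against.** A reader might infer that this analysis systematically reverses the drug effect, or that a short time mostly marks failure. The documents do not support that. Section 11.2 leaves dosing after re-escalation to the clinician, so re-tapering is allowed and brings the hazard ratio near or above 1. At recurrence rates that give about 4 v 2 mg with the re-escalated dose held, there is no reversal. Section 2 says historical data are insufficient, so no recurrence pattern can be called the expected one. What stands is that the sign depends on unknowns unrelated to benefit.

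The second objection is that little rests on this result. Section 11.8 says no formal efficacy comparison will be made. Time to final dose is not an endpoint in Section 2.2.2.2, a success criterion in Section 9.1 or the basis of the sample size. Final dose and cumulative dose, which have a clear direction, are reported beside it. This is right and limits the severity. It also rules out saying that the analysis would misdirect the definitive trial, since no decision rule uses the hazard ratio.

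The third objection is that a later analysis plan could define the event. It could settle whether reaching a dose means the first day at it or the day from which it is kept. It could not make the patient's own final dose a common target without changing the comparison that the protocol names.

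**Conclusion.** The point holds as a minor one. The event days follow from the protocol alone: Day 1 for no reduction, Days 3, 5 and 7 for stopping at 6, 4 and 2 mg, and Day 9 at the earliest for complete withdrawal of dexamethasone, with no censoring among completers. The hazard ratio therefore has no fixed direction of benefit, and the default 1-sided p-value of Section 15.5 has no meaning for it.

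The hazard ratios themselves rest on assumed symptom-control and recurrence patterns and on assumed clinician behaviour after re-escalation. They show that the ratio can fall on either side of 1 for an effective drug. They do not predict the value this trial would observe.

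**What to change.** In Sections 2 and 14.4, replace time to final dose with time to a common prespecified analysis threshold, reached and held to Day 14, with non-achievers censored at Day 14. One example is 4 mg/day or less, which is 50% of the common 8 mg on-study start. Alternatively, drop the Cox comparison and rely on the final-dose and cumulative-dose analyses. Either way this is an analysis definition and changes no dosing rule. The cost is wording only, since dexamethasone administration is already collected (Section 14.3).

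Two obvious alternatives are weaker. Time to first re-escalation would count a patient who never reduces as a success, and adding death or withdrawal as an event would need a wider population than the completers of Section 15.5. A threshold of 50% of the pre-trial dose would give different targets, because entry doses run from 4 to 12 mg: a 12 mg entrant would meet it at 6 mg (Day 3) and a 4 mg entrant only at 2 mg (Day 7).

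The downside is that any threshold is a choice and ignores reduction below it, which the other two dose analyses cover. Events may also be few: in the base case with +4 mg held, 30% of 18 placebo patients is about 5 events, so the estimate should be reported as descriptive.

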2.1.3 Tertiary

- Describe endocrine, liver function and lipid profiles of patients on micronised progesterone and/or placebo (Stage 2)
- Ensure no undesired CT/MRI changes in tumours (size, enhancement pattern) whilst on micronised progesterone/placebo (Stage 2)
- Establish the acceptability and feasibility of PROMs (Stage 2)
- Evaluate the acceptability of a subsequent randomised controlled trial (Stage 2)

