2.2.2.3 Tertiary

- Confirmation that patients on micronised progesterone have no additional clinically significant changes in their endocrine, liver function or lipid profile.
- Description of changes on CT/MRI in patients on micronised progesterone compared to those on placebo
- Acceptability/feasibility of PROMs and future trial design, including randomisation, established through patient interviews.

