Appendix 5 – Stage 2: Schedule of activities

Dosing	Day -2 and -1	Day 1	Day 2	Day 3	Day 4	Day 5	Day 6	Day 7	Day 8	Day 9	Day 10	Day 11	Day 12	Day 13	Day 14	Days 15 - 21	Day 22 ⁸
Dexamethasone (mg) – non IMP	8	8	8	6 [#]	6 [#]	4 [#]	4 [#]	2 [#]	2 [#]	0 [#]	0 [#]	0 [#]	0 [#]	0 [#]	0 [#]	As clinically indicated	As clinically indicated
Micronised progesterone/ placebo t.d.s. - IMP		*	*	*	*	*	*	*	*	*	*	*	*	*	*		
Activity	Day -7 to Day -1																
Symptom directed physical examination	X	X							X						X		X
Medical History	X																
Pregnancy ⁵	X																
Neuro. exam ¹		X							X						X		X
Weight/BMI		X							X						X		X
BP, pulse, temp		X							X						X		X
AE review and Dex/IMP dose review	X		X		X		X		X		X		X		X	X ⁷	X
Concomitant Medications Review	X	X							X						X		X
Full blood count	X	X							X						X		X
Clotting profile	X	X							X						X		X
U & E, LFT, Ca	X	X							X						X		X
Hormone profile ²		X													X		

Progesterone/placebo PK blood samples ³		X							X						X		
Side-effects diary		X	X	X	X	X	X	X	X	X	X	X	X	X	X	X	X
Patient Interview ⁴																X	
DSQ-C		X													X		
EORTC QLQ-C30		X													X		
EORTC BN20		X													X		
CT/MRI brain ⁶	X														X		

On Day 3 to day 14, if clinically appropriate, the dexamethasone dose will be reduced by 2mg/day on alternate days and can be discontinued if indicated. See Appendix 7 Drug Table Stage 2 for further detail

* Dose determined in Stage 1 and modified as per protocol

¹ Neurological assessment will also be completed at any time dexamethasone dose needs to be increased

² Patient will be asked to fast (water only) and avoid taking their dexamethasone and progesterone/placebo before the blood sample is taken between 8.00am – 10.00am. After which they should take their prescribed dexamethasone and progesterone/placebo. "Hormone bloods" include: cortisol, glucose, testosterone, lipids; HbA1c, TSH, free T4, FSH, LH, oestrogen, IGF-1.

³ Trough progesterone and dexamethasone levels. Prior to dose of progesterone (or placebo) and dexamethasone. These will be between 8.00am-10.00 am where the patients will already be delaying taking the medication.

⁴ To be completed once between Day 15 and Day 21. Approximately 15 patients will be approached for the patient interview.

⁵ WOCBP – Woman of child bearing potential only

⁶ CT/MRI brain – Within 14 days of screening visit.

⁷ Alternate days.

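### The tertiary laboratory endpoint is comparative, but its listed analysis names only progesterone patients, so dexamethasone taper effects, at least on glucose and cortisol, cannot be told from drug effects

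*Protocol*

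**What the plan says.** Three places in the Protocol deal with the Stage 2 laboratory profiles.

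- **Aim (2.1.3):** "Describe endocrine, liver function and lipid profiles of patients on micronised progesterone and/or placebo (Stage 2").
- **Endpoint (2.2.2.3):** "Confirmation that patients on micronised progesterone have no additional clinically significant changes in their endocrine, liver function or lipid profile".
- **Analysis (14.4 Final analysis, tertiary endpoint):** "Presentation of relevant lab results to assess endocrine, liver function and lipid profiles in patients on progesterone".

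The next item in the same analysis list, on imaging, is "Comparison (progesterone v placebo) of CT/MRI data (including tumour size, enhancement pattern etc"). The secondary items on final dose, cumulative dose and time to final dose also name both arms.

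On dexamethasone, section 11.2 says: "From Day 3-14, if clinically appropriate, the dexamethasone dose will be reduced by 2mg/day on alternate days". Appendix 5 shows the full taper: 8 mg on Days 1 and 2, stepping down to 0 mg from Day 9. The hormone profile is scheduled on Days 1 and 14; its components "include: cortisol, glucose, testosterone, lipids; HbA1c, TSH, free T4, FSH, LH, oestrogen, IGF-1". Liver function tests are scheduled before treatment and on Days 1, 8, 14 and 22. The schedule makes no distinction between arms.

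**The concern.** The word additional in the endpoint needs a reference. In a placebo-controlled stage with 18 patients per arm (15.4), that reference is the placebo arm. The one analysis listed for the endpoint names progesterone patients and no others, so carried out as written it does not answer the question.

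This matters more here than in most trials because a second cause of laboratory change runs over the same 14 days. Hormones, glucose and lipids are measured only at the two ends of the period in which dexamethasone may be withdrawn. The side-effect table in 1.3.1 lists hyperglycaemia and, after stopping, adrenal insufficiency. Section 1.5.2 separately reports endocrine changes with long-term progesterone. A change from Day 1 to Day 14 in the progesterone arm could come from either source. A taper effect could be read as a drug effect, or could mask one. Safety at the selected dose is among the success criteria in 9.1, so the reading of these data may carry into the design of the next trial.

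**Working it through.** **The plan's own figures.** The Protocol states no figure for this endpoint. Its power statement (15.3) concerns dexamethasone dose. It reproduces (18 per arm, one-sided t-test at 0.05, noncentral t: 90.2% at effect size 1.00 and 80.3% at 0.85, against the stated 90% and 80%) but has no bearing here.

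**What each display estimates.** Write the mean Day 1 to Day 14 change as the sum of its causes, where D is the progesterone effect and T the taper effect in each arm:

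- progesterone arm: D + T(prog)
- placebo arm: T(plac)
- progesterone arm alone estimates D + T(prog)
- progesterone minus placebo estimates D + [T(prog) − T(plac)]

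The one-arm display carries the whole taper effect. The contrast removes the part common to both arms and leaves only any difference in taper effect.

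**Illustration of size.** The Protocol gives no laboratory means or SDs, so the taper shift is an assumption, shown over a range in units of the SD of change. Take D = 0 and the same taper shift m in both arms, with n = 18 per arm and a one-sided test at 0.05.

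One-arm before/after test: P(signal) = 1 − F(t(0.95; 17)), where F is the noncentral t distribution with 17 degrees of freedom and noncentrality m × √18 = 4.243 × m.

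| Shared taper shift m (SD) | Noncentrality | One-arm P(signal) | Between-arm P(signal) |
|---|---|---|---|
| 0 | 0 | 5% | 5% |
| 0.25 | 1.06 | 27% | 5% |
| 0.50 | 2.12 | 65% | 5% |
| 0.75 | 3.18 | 92% | 5% |
| 1.00 | 4.24 | 99% | 5% |

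The between-arm column stays at 5% because the expected difference is zero when D = 0 and the taper effect is equal.

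**Precision of the contrast.** With the plan's default 80% interval (15.5):

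- between arms: t(0.90; 34) × √(2/18) = 0.44 SD half-width
- one arm: t(0.90; 17) / √18 = 0.31 SD half-width

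The contrast is wider. It trades precision for removal of the shared taper effect, and it yields an estimate, not a confirmation.

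**Which analytes the documents support.** The corticosteroid table in 1.3.1 covers glucose (hyperglycaemia) and adrenal function, for which cortisol is in the panel. It lists no lipid or liver effect, and the Protocol does not say that the taper alters lipids, liver tests, gonadotrophins, TSH or oestrogen.

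**The case against.** The strongest reply is that this is loose wording. The bullet does not exclude placebo in terms; the list is introduced as non-exhaustive and is meant to address each endpoint; aim 2.1.3 mentions placebo; and a full statistical analysis plan is promised in 15.5. Other bullets, such as quality of life and percentage dexamethasone reduction, name no arm at all. It is therefore fair to accept that both arms may be intended, and a reader should not infer deliberate exclusion of the placebo data. But a bullet that names no arm leaves the matter open, whereas this one names a single arm. A non-exhaustive list permits a placebo comparison without providing for one.

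A reader might also see a direct conflict with 2.1.3. The and/or wording there can be met by describing one arm, so this is a loose mismatch.

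Second, the consequence is limited. Abnormal laboratory findings fall within the adverse event definition (12.1), all adverse events are graded and recorded in every patient (12.2), and an independent committee meets every six months (5.3). This stands and lowers the impact. It does not make the listed analysis fit its endpoint.

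Third, the taper is conditional, varies between patients and is recorded, so results can be read against dose received. That helps. But within one arm every patient is on progesterone and taper depth follows symptoms, so it does not replace the placebo reference.

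Fourth, a placebo contrast is not a complete cure. If progesterone spares dexamethasone, as the trial hopes, the arms will differ in taper depth and the difference will carry some of that. This is correct, and it is why dose received should be shown beside the results.

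**Conclusion.** The point holds as a mismatch between a comparative endpoint and an analysis bullet that names one arm. Followed as written, the bullet cannot separate taper from progesterone effects, at least for glucose and cortisol. The 27% to 99% range shows how far a one-arm reading could mislead; it rests on assumed shifts of 0.25 to 1.0 SD, equal tapering, 18 patients per arm and a formal test that the plan does not itself propose for these data.

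Two stronger readings are not supported. A reader might infer that every laboratory result is fully confounded with the taper: the documents give a corticosteroid mechanism only for glucose and adrenal function, and the taper is conditional. A reader might also argue that even no events among 18 patients leaves a wide upper limit: that describes the precision of any single arm and says nothing about the missing comparator.

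The impact is modest. The endpoint is tertiary and descriptive, no decision rule depends on it, and the placebo data are scheduled to be collected anyway.

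**What to change.** Change the laboratory bullet under 14.4 Final analysis to present endocrine, liver and lipid results by arm: Day 1, Day 14 and change from Day 1, with counts of clinically significant shifts in each arm and a descriptive progesterone minus placebo difference with the plan's 80% interval. Show dexamethasone dose received alongside, because taper depth may differ between arms.

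In 2.2.2.3, reword the endpoint from a confirmation to a comparison, since 18 against 18 gives an imprecise estimate.

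No new samples or visits are needed: Appendix 5 already schedules these bloods for all Stage 2 patients. The cost is two lines of wording, a little more tabulation, and a set of imprecise contrasts that should be labelled as descriptive.
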